Theoretical underpinnings of Resourcefulness Training posit that caregivers with greater resourcefulness will experience less stress and, as a result, will augment their caregiving capacity. This intervention involves the following components: 1) a face-to-face session for teaching social (help-seeking) and personal (self-help) resourcefulness skills **using a 32 minute video**, 2) ongoing access to video vignettes of parents of technology-dependent children describing the application of resourcefulness skills in daily life, 3) 4 weeks of skills' reinforcement using daily journal writing by the parents, and 4) weekly phone calls from the intervention nurse over 4 weeks after face-to-face intervention training. Booster sessions for the intervention group at 2 and 4 months post-intervention consist of a phone call and one week of journal writing. The Attention Control group will receive weekly phone calls for the first four weeks plus any usual care. In this exploratory stage of intervention work, we will evaluate the impact of the intervention on psychological and physical outcomes and family outcomes (family functioning) over time and whether changes in resourcefulness skills mediate these outcomes.

The specific aims of the study are to: Aim 1: Determine whether Resourcefulness Training versus Attention Control improves psychological (general mental health, depressive cognitions, depressive symptoms, appraised stress, burden) and physical outcomes (general physical health, chronic stress [hair cortisol]) and family outcomes (family functioning) over 6 months in parents of technology dependent children, after controlling for the parents' race/ethnicity, sex, family income, and children's functional status. Aim 2: Determine whether changes in psychological and physical outcomes and family outcomes are mediated by changes in parents' levels of resourcefulness (personal and social).

Background

1. Describe the relevant prior experience and gaps in current knowledge describing how it will add to existing knowledge.
2. Describe any relevant preliminary data.

Please add relevant references at the end of the protocol, not at the end of this section.

Introduction/Background

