Level of Technology Dependency Questionnaire will be used to determine group assignment (Group 1 mechanical ventilators; Group 2 intravenous administration of nutritional substances/drugs; Group 3 respiratory/nutritional support equipment). Past studies of this population have used this rubric.¹⁴

Resourcefulness Skills Scale is an 8-item questionnaire ($\alpha=.78$) that will assess the fidelity of the Resourcefulness Training (RT) intervention.³⁰ Participants are asked the frequency of use for each of the items taught in the RT intervention from never (0) to always (3). Higher scores indicate greater use of resourcefulness skills.³⁰

Parent Inventory for Parents (PIP) is a 42-item scale ($\alpha=.80-.96$) that assesses parenting stress (frequency, difficulty) of caring for a chronically ill child; higher scores indicates greater stress Construct validity was established by significant corelations with state anxiety and general measures of parenting stress.

Chronic Stress will be measured by a hair cortisol sample.

Caregiver Burden will be measured using the Zarit Burden Interview-12 ($\alpha=.85-.89$), a 12-item tool that assesses the burden people feel when taking care of another person; higher scores indicates higher burden.

Qualitative Assessment of Feasibility, Acceptability, and Fidelity of RT will be assessed by audio-recording **participant’s responses** to: “Tell me what it was like for you to (a) do expressive writing and (b) apply RT?”, “What parts were easiest/most challenging?”, “What part of RT was most/least interesting?”, “Did you learn all parts of RT?”, “How can we enhance RT teaching/learning in the future?” “Any parts of the intervention (ie. teaching or intervention materials) or follow up you think we can modify to appeal more to male caregivers?” The **research team responses** will be assessed by analysis of journal entry responses to the following questions on at least a bimonthly basis: “What parts of teaching RT were easiest/most challenging?,” “Was any portion of the intervention omitted?,” “Is the timing of data collection appropriate?,” “What portion (if any) of the intervention needs to be modified?,” “What challenges (if any) have there been with study recruitment?,” “Has any group contamination been noted?,” “Describe rate of and reasons for attrition.” “What challenges have occurred with the follow-up data collection?”

Table 1: Study Tools and Measures

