Variable	Measure (Appendix A)	Time of measure				Reliability in previous studies		
Outcome Variables: Parent		Enroll 6 Wk						
		3M	6M					
Psychological and Physical Health	Medical Outcomes Short Form Health Survey (SF-12 version 2)	X	X	X	X	$\alpha=.85-.93$		
Depressive Cognitions	Depressive Cognition Scale	X	X	X	X	$\alpha=.75-.93$		
Depressive Symptoms	Center of Epidemiological Studies- Depression Scale (CES-D)	X	X	X	X	$\alpha=.84-.93$		
Stress	Pediatric Inventory for Parents (PIP)- subjective Hair Cortisol- objective	X	X	X	X	$\alpha=.80-.96$		
		X		X	X	Sensitivity/Specificity=100%		
Burden	Zarit Burden Interview-12	X	X	X	X	$\alpha=.85-.89$		
Outcome Variable: Family		Enroll 6 Wk						
		3M	6M					
Family Functioning	Feetham Family Functioning Survey	X	X	X	X	$\alpha=.73-.83$		
Mediating Variable		Enroll 6 Wk 3M 6M						
Resourcefulness: Personal	Resourcefulness Scale (Personal Resourcefulness Subscale)	X	X	X	X	$\alpha=.83$		
Resourcefulness: Social	Resourcefulness Scale (Social Resourcefulness Subscale)	X	X	X	X	$\alpha=.79$		
Covariates		Enroll 6 Wk 3M 6M						
Parent: · Race/Ethnicity, Gender, Family Income		Enrollment form		X		IRR=1.0		
Technology-Dependent Child: · Functional Status		Functional Status II- Revised		X	X	X	X	$\alpha=.76-.80$
Sample Characteristics		Enroll 6 Wk 3M 6M						
Parent: · Age, Marital Status, Duration of Tech. Dependent Child Caregiver Role		Enrollment form		X			IRR=1.0	
· Education, Amount of Home Nursing Support Services, Lay Caregiving Assistance		Enrollment form		X	X	X	X	IRR=1.0
· Interpersonal Support		Interpersonal Support Evaluation List		X	X	X	X	$\alpha=.88-.90$
Technology-Dependent Child:								

Age	Enrollment form	X				IRR=1.0
Type of Medical Technology Used	Technology Dependency Questionnaire	X	X	X	X	NA

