Hair sample for cortisol level, audio recording with only subject ID number for exit interview regarding intervention for intervention group only. Questionnaires will be administered as well.

Data Analysis Plan

1. *Describe the data analysis plan, including any statistical procedures. Provide a power analysis if applicable.*
2. *If applicable, describe the primary and secondary study endpoints including safety endpoints.*

ANALYSIS. All data will be entered into UH REDCap and cleaned. We hypothesize that parents receiving the Resourcefulness Training intervention will have significant improvement in parental outcomes (psychological and physical) and family outcomes (family functioning) compared with parents in the Attention Control arm. We also hypothesize that resourcefulness will mediate the effect of the intervention on all study outcomes.

Preliminary Analyses. Exploratory data techniques will be used to examine univariate characteristics (central tendency, dispersion, and distribution) of demographics and covariates measured upon randomization in each arm. These exploratory techniques will be based on proportions (in the case of dichotomous variables) and medians and/or means (in the case of variables measured on an interval scale). Due to randomization, no formal tests of these variables will be performed because any imbalance between arms is known to be due to chance. Profile plots will also be used to describe the participant-specific (parent) and arm-specific trends for each outcome over the four time points.

Primary Analyses.

Aims 1 & 2: Analysis of the monthly rate of change in each of the parent outcomes in each arm will be estimated via linear mixed models and fit using SAS PROC MIXED.108,109 Each model will include a random intercept and slope (possibly modeled using a polynomial spline) to account for between-subject variance in each outcome over time. Conditional on these random effects, we will also explore within-subject variance in

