each outcome over time using different residual covariance structures and select the most appropriate structure using likelihood-based criteria. Fixed effects will include a continuous variable to represent time since randomization, an indicator variable to represent the intervention, and stratification factors used during randomization (facility, OTA technology group, sex and race/ethnicity). Assuming a linear rate of change over time, the regression coefficient of the terms representing interactions between time and the intervention indicator variable will be used to estimate the difference in the monthly rate of change in each outcome between the two arms.

To determine if resourcefulness mediates the effect of the resourcefulness intervention on parent outcomes, a model-based causal mediation model^{110,111} will be fit using separate generalized linear models of parent outcomes at 3 months after randomization that adjust for the intervention indicator variable, stratification factors, and the mediator at 6 weeks after randomization. This model will allow us to decompose the total effect of the resourcefulness intervention on maternal outcomes at 3 months into direct and indirect (or mediated) effects and will allow us to estimate the proportion of the total effect that is mediated. Variance estimates, and consequently 95% confidence intervals, will be estimated using a bootstrapping procedure based on 1000 bootstrap samples. To more fully explore the temporal pattern of mediated effects, we will use similar models to also estimate the mediated effect using measurements of the mediator and maternal outcome taken at other time points as well (e.g., total effect of resourcefulness intervention on parent outcomes at 6 months that are mediated by personal or social resourcefulness at 3 months).

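### If a hair sample covers more than about 7 weeks, part of the 3-month hair cortisol value predates the 6-week mediator, so the main Aim 2 pairing can lose its time order for this one outcome

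*Combined protocol and SAP*

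**What the plan says.** Aim 1 (Objectives) counts hair cortisol among the physical outcomes, and Aim 2 carries it forward. The Measures/Instruments section gives it one sentence: "Chronic Stress will be measured by a hair cortisol sample". Table 1 lists it under the parent outcomes as "Hair Cortisol- objective", with samples at enrollment, 3 months and 6 months and none at 6 weeks. Under Confidentiality of Specimens and Banking, samples are labelled with ID and the time point of collection, and are sent to the laboratory in one batch after final data collection. No length of hair, segment, growth rate or period covered is given anywhere.

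The Data Analysis Plan hypothesizes that "resourcefulness will mediate the effect of the intervention on all study outcomes". The main mediation analysis models "parent outcomes at 3 months after randomization that adjust for the intervention indicator variable, stratification factors, and the mediator at 6 weeks after randomization". Other time points are to be explored afterwards, and the example given is the "total effect of resourcefulness intervention on parent outcomes at 6 months that are mediated by personal or social resourcefulness at 3 months". Nothing is said about hair cortisol being handled differently. The plan closes with a sensitivity analysis asking how strong an unobserved confounder would have to be to remove a mediated effect.

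**The concern.** A mediation claim needs the mediator to come before the outcome. For a questionnaire completed at 3 months, resourcefulness at 6 weeks does come first. Hair cortisol is used here as a marker of chronic stress, so a sample summarizes some stretch of time before it is cut. The documents do not say this outright; it follows from what the measure is used for. If the stretch is long enough, the 3-month value includes stress from before week 6.

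A parent whose stress eased early for any reason might then report more resourcefulness at week 6, and that same early easing would also be inside the 3-month cortisol value. The model would credit resourcefulness with an effect that ran the other way. Hair cortisol is the measure that Table 1 labels objective, so a mediated effect on it is likely to carry weight.

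**Working it through.** The documents give no figure on this point, so there is none to reproduce. The visit times come from the plan. The window length w is an assumption, shown over a range.

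**1. Inputs.** Mediator at M = 6 weeks and outcome at T = 3 months (main pair). Mediator at 3 months and outcome at 6 months (the pair named as an example). One month = 4.348 weeks, so 3 months = 13.04 weeks and 6 months = 26.09 weeks.

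**2. Formula.** A sample cut at T covers T − w to T. Time before the mediator = max(0, M − (T − w)). Share = that time / w.

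**3. Threshold for the main pair.** Overlap starts when w exceeds T − M = 13.04 − 6 = 7.04 weeks, or 7.04/4.348 = 1.62 months. For the 3-month/6-month pair it starts when w exceeds 26.09 − 13.04, that is, 3 months.

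**4. Share of the sample that predates the mediator.**

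| Assumed window | 6-week mediator, 3-month hair | 3-month mediator, 6-month hair |
|---|---|---|
| 1 month | 0% | 0% |
| 2 months | (6 − 4.35)/8.70 = 1.65/8.70 = 19% | 0% |
| 3 months | 6.00/13.04 = 46% | 0% |
| 3.75 months | (6 + 3.26)/16.31 = 9.26/16.31 = 57% | (13.04 − 9.78)/16.31 = 3.26/16.31 = 20% |

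The last row is a 3 cm segment at an assumed growth of 0.8 cm per month: 3/0.8 = 3.75 months.

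**5. What the overlap adds (illustrative).** Let the cortisol value be f × early stress + (1 − f) × late stress, where f is the share from step 4. Suppose resourcefulness has no effect on stress and is itself influenced by early stress. Let early and late stress have equal variance and within-arm correlation r. The within-arm covariance of mediator and outcome is then proportional to f + (1 − f)r.

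- r = 0: from 0 without overlap to 0.46 at f = 0.46.
- r = 0.5: from 0.50 without overlap to 0.46 + 0.54 × 0.5 = 0.73.

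So with r = 0.5 a false association is present even without overlap, and a 46% overlap makes it 0.73/0.50 = 1.46 times as large. I give no percentage for falsely mediated effect. It would depend on r and on how strongly early stress influences resourcefulness, and the documents give neither.

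**The case against.** The strongest reply is that everything depends on a window that the documents do not state. Below about 7 weeks there is no overlap. Only one outcome is affected, in work that the protocol calls exploratory, and the better pair is already planned. All of this is true. It limits the size of the point, but nothing in the plan keeps the window under 7 weeks.

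A second reply is that the planned sensitivity analysis covers the problem, because early stress acts as a common cause of mediator and outcome. It does bear on the mechanism. But early stress is itself affected by the intervention and is a component of the outcome, so an analysis framed around an unobserved outside confounder gives only partial protection.

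A third reply is that changing the pair does not remove ordinary confounding. This stands: step 5 shows the part due to r remaining when f = 0, and questionnaire outcomes share it.

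A reader might also infer that the Aim 1 monthly rate of change in cortisol is understated, since the model dates samples by visit ("Fixed effects will include a continuous variable to represent time since randomization"). The documents do not support that as a general statement. With samples at 0, 3 and 6 months, the least-squares slope is (last − first)/6. For a 3-month window:

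- Arm difference growing linearly from randomization: sample means 0, 1.5, 4.5; slope 4.5/6 = 0.75 against a true 1.
- Immediate, sustained difference: 0, 1, 1; ratio 1.00.
- Rise to 3 months, then flat: 0, 0.5, 1; ratio 1.00.
- Peak at 3 months fading to half: 0, 0.5, 0.75 against 0, 1, 0.5; ratio 0.75/0.5 = 1.50.

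The plan does assume a linear change. But the main training ends at 4 weeks and the boosters are meant to prevent decline, so an early effect that is then held is at least as plausible. Re-dating the samples to 0, 1.5 and 4.5 months would not be a safe remedy. It corrects the linear case, but moves the immediate effect from 1.00 to 1.14 (slope 2/10.5 = 0.190 against 1/6) and the fading one from 1.50 to 1.86.

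**Conclusion.** The point holds in a conditional form. The plan applies the 6-week/3-month pair to hair cortisol without stating what period a sample represents. If that period exceeds about 7 weeks, the time order that Aim 2 needs can fail for this outcome, with 19% of the 3-month value predating the mediator at a 2-month window and 46% at 3 months. At 1 month there is no problem. The conclusion rests on reading chronic stress as a look-back measure and on assumed windows.

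It would go too far to say that the time order is broken, because that depends on the unstated window. Nor can the whole of any false mediation be put down to the overlap, which adds to ordinary confounding. No claim about the direction of bias in the monthly rate of change follows.

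**What to change.** For hair cortisol only:

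1. Make resourcefulness at 3 months with cortisol at 6 months the main mediation analysis, and state that the 6-week/3-month pair will not be interpreted as mediation for this outcome.
2. Specify one scalp-end segment for all samples, short enough to cover at most 3 months, and set it before the batch assay. This is the condition under which item 1 works. A 3 cm segment would not meet it at an assumed 0.8 cm per month (3.75 months, 20% overlap); at that growth rate the limit is 3 × 0.8 = 2.4 cm.

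Leave the time variable in the slope model as planned.

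The cost is a few lines in the analysis plan and one in the hair procedure, with no new samples or visits. Because the samples are held for a single shipment, the segment can still be fixed before assay, provided the scalp end of each stored sample can be identified. The downside is that parents lost between months 3 and 6 drop out of this analysis; the plan allows for 10% attrition overall, and this loss would be part of it. Even beyond 3 months the exchange is favorable: at 3.75 months the overlap is 20% rather than 57%.

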In controlled, experimental trials, RT was found to significantly improve resourcefulness,³⁻⁵ adaptive functioning and life satisfaction¹⁵ in elders. RT also improved negative emotions, functioning and depressive cognitions up to 12 weeks post intervention.⁶ While past studies of RT have used a group teaching format/videoconferencing,⁴ two current studies are examining the efficacy of RT using an in-person individual format including grandmothers raising grandchildren.¹⁶ This format is based on research indicating stronger effects for individualized interventions¹⁶. Additionally, this study includes an opportunity to practice and reinforce RT skills taught using expressive writing (EW); personal journaling about specific events. EW has been found to significantly improve physical and psychological health and reduce negative emotions as well as health care visits.¹⁷ While RT has not been tested in young caregivers, equivocal effectiveness is anticipated.

Although children with special health care needs comprise only 16.2% of all children under 18 years, they accounted for 45.5% of the medical expenditures in 2000 due to significantly more out-patient visits, hospitalization, and medications than other children.¹⁸ Children who are technology dependent, while small in number, consume a large proportion of the health care dollars, yet little research has been done to examine how to help promote positive family functioning that will assist in better care for their child.

The study model is based on resourcefulness theory.¹⁹⁻²⁰ Major constructs in the model represent contextual factors, process regulators, resourcefulness (personal, social), and quality of life outcomes. RT is proposed to directly affect all model constructs except contextual factors as indicated by dashed lines. **Contextual factors** include mother’s variables (age, race, income, education), child’s variables (age, level of technology dependence, functional status) and caregiving situation (duration of care, amount of home health care nursing). **Process regulators** (depressive cognitions, depressive cognitions, burden, stress) include variables that mediate effects of contextual factors on resourcefulness. Depressive cognitions are thought patterns that

may lead to depression.²² Assertions that cognitions influence resourcefulness has been validated in women caregivers.¹⁹

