Resourcefulness is an “acquired repertoire of skills and behaviors necessary for the successful execution of self-control behavior.”^{19 p.26} These skills are learned throughout life by informal training or may be taught in cognitive behavioral programs and include the belief that one is able to cope effectively despite adversity.¹⁹ Skills of self-instruction, problem-solving, belief in coping effectiveness are used to control the effects of disturbing feelings, thoughts and sensations on performance of daily tasks.¹⁹ Zauszniewski’s²⁰ model includes personal resourcefulness (self-help) and social resourcefulness (help-seeking) that are beneficial for maintaining healthy physical and psychological functioning across the lifespan. Resourcefulness training (RT) includes teaching positive self-talk, problem-solving and priority setting.¹⁵

Empirical evidence indicates that resourcefulness is a significant predictor of quality of life for non-caregivers/caregivers.^{19, 23} **Parent outcomes** are conceptualized as absence of depressive symptoms, positive family functioning, better self-assessed health. **Depressive symptoms** include depressed mood and feelings of helplessness and hopelessness.¹⁰ Greater resourcefulness is a significant predictor of a decreased level of depressive symptoms.²⁵ Conversely, less resourcefulness contributed to perceptions of worse family functioning in grandmothers raising grandchildren.¹⁷ **Family functioning** is a parent’s perception and level of satisfaction with relationships between the family and individuals as well as subsystems and the community. **Self-assessed health** is the mother’s perception of her health and includes both physical and psychological well-being.²⁷ Based on the theoretical and empirical literature, the study model proposes that contextual factors, process regulators, and resourcefulness all directly affect quality of life outcomes.

Inclusion and Exclusion Criteria

1. Describe how individuals will be screened for eligibility.
2. Describe the criteria that define who will be **included** in your final study sample.

	Inclusion
1.	Parents who are at least 18 years of age
2.	Parents caring for a child age 16 years and younger at home who is technology-dependent (Group 1 mechanical ventilators; Group 2 intravenous nutrition/medication; Group 3 respiratory or nutritional support);
3.	Able to speak, write and understand English.
4.	

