Research Design. A quasi-experimental RCT design with random assignment will be used to test the efficacy of a Resourcefulness Training (RT) intervention compared with an attention control group in mothers and fathers of technology-dependent children. All participants will receive a face-to-face visit from study staff for the T1 data collection. In addition, the intervention group will receive individually tailored RT web based instruction via an approximately 30 minute video that provides details on each of the 8 resourcefulness skills with short examples of application, instruction on journal writing to practice and reinforce use of resourcefulness skills, access to video tapes of parents describing application of resourcefulness skills in the care of their technology-dependent child. Parents will be asked to provide their email address so that we may send them invitation for access to the website that they may visit at any time to access the video tapes. Data will also be collected face-to-face at 3 months (T3) and 6 months (T4) post-intervention. At 6 weeks parents will be emailed a link to the REDCap survey for Time 2 data collection and contacted by phone for SF-12 survey with email reminders. Open-ended questions following their final data collection appointment will allow mothers/fathers to discuss feasibility, acceptability, and fidelity of this intervention and suggestions for potential modification of the intervention and follow up procedures. For this study, 99 female participants and 24 male participants are expected to be enrolled that takes into account 10% attrition.

Measures/Instruments.

The **Depressive Cognition Scale** an 8-item scale ($\alpha = .75$), will measure depressive thought patterns that may lead to depression.⁸ Responses on a 6-point scale range from strongly agree (5) to strongly disagree (0) with a score range 0-40. Items include depressive cognitions such as hopelessness and worthlessness; higher scores indicate more depressive cognitions.

The **Resourcefulness Scale**, a 28-item scale ($\alpha = .85$), will assess both personal (16 items) and social (12 items) resourcefulness.⁹ Responses on a 6-point scale range from extremely descriptive (5) to not descriptive (0) with a score range 0-140; higher scores indicate greater resourcefulness. Construct validity was assessed using confirmatory factor analysis.

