To account for any multiple comparisons, a Bonferroni-corrected two-sided significance level will be applied to all analyses for all aims. Additionally, as with any study, we expect some level of missing data at each time point. To adjust for the missing data in all mixed-models analyses, we will use pattern-mixture models. This modeling approach will be applied to each model to ensure that missing data is adequately accounted for in each analysis. In contrast to a “completers only” approach, pattern-mixture models will provide a consistent and asymptotically efficient estimate of the effect of intervention on the monthly rate of change in parent and family outcomes when data is missing not at random.

Secondary Analyses. To obtain more precise estimates of the intervention effect on the time point interval rate of change in each parent or family outcome, additional multivariable analyses will characterize and estimate the relationship between potential covariates at baseline and each outcome. For continuous variables that do not have a linear relationship with the outcome, appropriate transformations or categorization will be considered. For nominal and ordinal variables, the number and type of categories will be considered to obtain

the optimum relationship, if any, with the outcome. Based on a two-sided significance level of 0.15, any baseline covariate found to be associated with the outcome will be included in the model described for the Primary Analyses.

Modification of the intervention effect on the monthly rate of change in each parent outcome will also be tested in each model by including an interaction between a pre-specified effect modifier measured at baseline, the intervention indicator variables, and the variable representing time since randomization. Should an interaction be detected based on a two-sided significance level of 0.05, the monthly rate of change in each outcome will be estimated in each of the arms for each level of a categorical effect modifier or at the 25th, 50th, and 75th percentiles of a modifier that is measured on an interval scale.

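### The Aim 2 mediation models leave out baseline resourcefulness and the baseline outcome, so correlation that existed before training can be counted as mediation

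*Combined protocol and SAP*

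**What the plan says.** Aim 2 (Objectives) is stated in terms of change: "Determine whether changes in psychological and physical outcomes and family outcomes are mediated by changes in" the parents' personal and social resourcefulness.

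The mediation paragraph under Primary Analyses in the Data Analysis Plan relates one level to another. It models each parent outcome at 3 months, and the models "adjust for the intervention indicator variable, stratification factors, and the mediator at 6 weeks after randomization". The stratification factors are listed just before as facility, technology group, sex and race/ethnicity. The covariates of the mediator model are not listed separately. Analyses at other time points, such as the 3-month mediator with the 6-month outcome, use similar models, so the same covariate set carries over.

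Table 1 schedules both resourcefulness subscales and every outcome, including hair cortisol, at enrolment. T1 data collection comes before the intervention.

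Three other provisions bear on the point:

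- Multiplicity: "a Bonferroni-corrected two-sided significance level will be applied to all analyses for all aims". The divisor is not given.
- Secondary Analyses: a screen at p<0.15, after which "any baseline covariate found to be associated with the outcome will be included in the model described for the Primary Analyses".
- A sensitivity analysis for the mediation models, asking how strong an unobserved confounder would have to be to make a mediated effect non-significant.

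**The concern.** The indirect effect combines two paths: training to resourcefulness, and resourcefulness to outcome. Random allocation identifies the first. The second is an observational association within arms, and it is confounded by anything that drives both 6-week resourcefulness and the 3-month outcome.

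The protocol's own theory says that the T1 scores are such confounders. The study model in the Justification section places depressive cognitions, burden and stress upstream of resourcefulness, and all three are also Aim 1 outcomes. It adds: "Assertions that cognitions influence resourcefulness has been validated in women caregivers". The same section then says: "Greater resourcefulness is a significant predictor of a decreased level of depressive symptoms". It also reports that training has improved resourcefulness in earlier trials. A parent who starts with low resourcefulness and high depressive symptoms will tend to keep both. A model without T1 scores reads that persistence as an effect of resourcefulness on the outcome and multiplies it by the training effect.

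At stake are the direct and indirect effects and the proportion mediated, which are what Aim 2 delivers under Primary Analyses. The Background section says that the results are to inform a larger trial.

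**Working it through.** The plan states no figure for the mediation analysis, so there is none to reproduce. The check derives the bias algebraically and then simulates the planned procedure.

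**Inputs from the protocol**

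- Sample size: the Research Design section expects 99 women and "24 male participants are expected to be enrolled that takes into account 10% attrition". That is 123 enrolled; 123 x 0.9 = 110.7, taken as 110, allocated 1:1.
- Interval: 95%, bootstrap, 1000 samples (Primary Analyses). The percentile form is assumed.
- Signs only: training raises resourcefulness, and higher resourcefulness goes with fewer depressive symptoms (Justification section).

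**Assumed inputs, all in SD units**

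- rho: T1 correlation of mediator and outcome, given the stratification factors
- s: stability of each score from T1 to follow-up
- a: training effect on the 6-week mediator
- b: true effect of mediator on outcome

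**Model.** With T1 scores M0 and Y0 correlated rho, arm A, and residual variance 1 - s^2:

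- M1 = s x M0 + a x A + error
- Y = s x Y0 - 0.3 x A + b x M1 + error

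Within arm, M1 has variance 1 and its covariance with Y is b + s^2 x rho. The written model therefore estimates a mediator coefficient of b + s^2 x rho instead of b:

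- expected indirect effect = a x (b + s^2 x rho)
- truth = a x b
- bias = a x s^2 x rho, which does not shrink with sample size

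**No true mediation (b = 0), a = 0.5, 2,000 simulated trials per row**

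| rho, s | Bias = a x s^2 x rho | 95% intervals excluding 0, as written | Same, with both T1 scores | Proportion mediated if total is -0.3 SD |
|---|---|---|---|---|
| -0.2, 0.5 | 0.5 x 0.25 x (-0.2) = -0.025 | 6.0% | 4.0% | 0.025/0.3 = 8% |
| -0.4, 0.6 | 0.5 x 0.36 x (-0.4) = -0.072 | 22.3% | 4.8% | 0.072/0.3 = 24% |
| -0.5, 0.7 | 0.5 x 0.49 x (-0.5) = -0.1225 | 53.1% | 5.1% | 0.1225/0.3 = 41% |

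A separate 1,000-trial simulation of the last two rows gave means of -0.073 and -0.122 SD, with 22.2% and 53.9% of intervals excluding zero. With both T1 scores added, the mean returns to about 0.

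**Weaker and null cases, as written**

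- a = 0.3 with (-0.4, 0.6): 0.3 x 0.36 x (-0.4) = -0.043 SD; 10.0% of bootstrap intervals exclude zero, against 1.8% with both T1 scores.
- a = 0.3 with (-0.2, 0.5): 0.3 x 0.25 x (-0.2) = -0.015 SD; 2.8%.
- rho = 0: mean 0.002 SD, 3.2%. a = 0: mean 0.001 SD, 1.1%. Both used a Monte Carlo 95% interval.

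**Bonferroni levels.** The divisor is assumed: 8 for the outcomes alone, or 16 for 8 outcomes x 2 mediators. These rates use a 20,000-draw Monte Carlo interval, because a 1000-sample percentile bootstrap at 0.05/16 leaves only about 1000 x 0.003125/2 = 1.6 resamples in each tail.

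| Level | Nominal | (-0.2, 0.5) | (-0.4, 0.6) | (-0.5, 0.7) |
|---|---|---|---|---|
| 0.05/8 | 0.6% | 0.55% | 4.3% | 18.5% |
| 0.05/16 | 0.3% | 0.4% | 2.25% | 11.75% |

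**True mediation present (a = 0.5, b = -0.3, truth -0.15 SD).** The formula gives 0.5 x (-0.3 + s^2 x rho) = -0.175, -0.222 and -0.2725, which is 17%, 48% and 82% too large. Simulated means were -0.175, -0.223 and -0.272 as written, and -0.149, -0.149 and -0.151 with both T1 scores. In the middle setting the sampling SD fell from 0.098 to 0.069.

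**The case against.** **The size is undocumented.** This stands. All inputs except the sample size and the interval are assumed, and at the weak end the distortion is negligible. The protocol gives a direction for depressive symptoms, family functioning and cognitions, but none for hair cortisol, physical health or burden. A correlation of opposite sign would mask mediation. Only the mechanism is certain, together with its sign where the baseline sign is known.

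**Bonferroni protects against false claims.** In part. In the weakest setting the rate is near nominal, but in the stronger settings it is many times nominal. The correction does nothing for the estimate or the proportion mediated, and the mediation paragraph itself specifies 95% intervals.

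**The sensitivity analysis would expose fragile results.** It might. It asks about unobserved confounders, however, and these are observed. With no true mediation, the omitted T1 scores alone leave a residual mediator-outcome correlation of s^2 x rho = -0.05, -0.14 and -0.245 in the three settings. The reported estimate stays uncorrected.

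**The p<0.15 screen might admit the T1 scores.** The wording is loose enough to allow that reading. The screen is nevertheless a secondary analysis aimed at rate of change, it names neither score, and in that model the T1 outcome appears to be one of the repeated responses.

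**Either T1 score alone is enough.** True in this simulation, where each blocks the single path from M0 through the correlation to Y0. It fails if T1 distress also affects later resourcefulness directly, or T1 resourcefulness affects the later outcome directly, and the protocol's theory proposes both.

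**The sample may be 94.** The Objectives section says so. At 94 the three rates are about 4%, 20% and 42%, and the bias is unchanged.

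**This is an exploratory pilot and the main purpose is efficacy.** Aim 1 is indeed untouched. Mediation is still one of two specific aims and sits under Primary Analyses.

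**Conclusion.** The concern holds. The listed covariate set omits two confounders that the protocol's own theory identifies and its own schedule measures, and nothing else in the plan reliably adjusts for them. For any outcome correlated with resourcefulness at T1, the indirect effect and proportion mediated will be biased by a x s^2 x rho if training raises resourcefulness. Under the assumed settings this runs from a trivial 0.015 SD to about 0.12 SD. There is no spurious mediation if either the correlation or the training effect on resourcefulness is zero, so the size will differ across the eight outcomes in Aim 1. These figures assume linear models, equal stability of mediator and outcome, and no confounding arising after baseline. The estimated total effect and the Aim 1 comparisons are not affected. Because the affected quantities are what Aim 2 reports, this should be corrected before the analysis.

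**What to change.** In the mediation paragraph, state that at every lag both the mediator model and the outcome model include the T1 value of the mediator (the matching personal or social subscale) and the T1 value of the outcome, alongside arm and the stratification factors. List the mediator model's covariates explicitly. State that these two covariates are fixed in advance and do not depend on the p<0.15 screen. Run the sequential-ignorability sensitivity analysis on the adjusted models, so that it addresses only confounding that remains unmeasured.

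The cost is one or two sentences, two degrees of freedom per model and no new data collection. In the simulated middle setting precision improves as well. Two limits remain and should be acknowledged in the report: confounding that arises between T1 and 6 weeks, and incomplete adjustment because the T1 scales are measured with error (Table 1 gives reliabilities of .83 and .79 for the two subscales).
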